# 2.3. RESEARCH HYPOTHESISES

Two main research questions are formulated regarding the effectiveness of ATM versus a standard treatment regimen consisting of acupuncture and stretching, but also the effectiveness of ATM as monotherapy, which will be investigated through appropriate statistical controls. The formal basis of statistical tests is the null hypothesis under which there is no association between the exposure and the outcome (Killeen, 2005). Starting from the assumption of no relationship, statistical tests quantify the probability that the observed relationship was observed by chance, due to the random sampling distribution. When the null hypothesis cannot be rejected then the observed relationship is attributable to chance rather than a true effect of the exposure on the outcome (Banerjee *et al.*, 2009).

Thus, the null hypotheses to be tested are formulated as follows:

- Research question 1: Effectiveness of ATM (intervention group before the intervention vs. the same group after the intervention)
  - Null hypothesis H0A1: The application of ATM does not affect the pain sensitivity assessed by the Pain Pressure Threshold (PPT) measured

with the pressure algometer (Commander Algometer) in patients with chronic neck pain (main hypothesis).

- Null hypothesis H0A2: The application of ATM does not affect the cervical range of motion (ROM) recorded with the Moover threedimensional (3D) Inertial Motion sensor in patients with chronic neck pain (secondary hypothesis).
- Null hypothesis H0A3: The application of ATM does not affect the strength of deep neck flexor muscles as measured by the Chattanooga Stabilizer Pressure Biofeedback in patients with chronic pain in the cervical spine (secondary hypothesis).
- Null hypothesis H0A4: The application of ATM does not affect the respiratory function assessed by the portable spirometer (MIR Spirodoc) in patients with chronic neck pain (secondary hypothesis).
- Null hypothesis H0A5: The application of ATM does not affect the pain in the cervical spine in terms of its intensity and quality, i.e., its sensory, emotional and behavioral dimensions using the McGill Pain Questionnaire-short form (SFMPQ) in patients with chronic neck pain (secondary hypothesis).

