2013). The first assessor will administer the consent form, the demographic characteristics form, the questionnaires and recorded the primary outcome measures, as well as the secondary outcome measure prior to the start of the study. The second assessor will administer the compliance and complaint form to the participants and will record the primary outcome measure and the secondary outcome measures after the completion of the interventions. Data analysis will be performed by an independent biostatistician, an associate of the Musculoskeletal Physiotherapy Research Laboratory of the University of West Attica (UNIWA), who will not know the group in which each participant will have been allocated.

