#### 2.5.3.1. PRIMARY OUTCOME MEASURE

#### 2.5.3.1.1. PAIN SENSITIVITY (PRESSURE ALGOMETER)

The primary outcome measure will be the pain sensitivity and a pressure algometer (Commander® Algometer, JTECH Medical, Midvale, Utah) will be used, measuring the Mechanical Pain Threshold (MPT). This model is a handheld algometer with two different heads (with surface of 0.5 cm^2, 1 cm^2), a flat pad and a fingertip adapter. The maximum input force reaches 111 N, while the wireless radio frequency (RF) reaches 2.4 GHz. The head which will be used has an area of one square centimeter (1cm^2) and the unit of measurement for the MPT value is kilogram per square centimeter (kg/cm^2).

In this PhD thesis, the recording of the pain sensitivity will be performed at specific points such as the upper part of the trapezius muscle and the suboccipital region, as the pressure algometer has shown high intra-rater reliability when applied to the upper trapezius muscle (Intraclass Correlation Coefficient / ICC: 0.85-0.86) and the suboccipital region (ICC: 0.84-0.93) in patients with chronic non-specific neck pain (Pérez-Martínez *et al.*, 2020). The measurement in the suboccipital region will be performed at the mastoid process and at the BL 10 point, which is located on the horizontal line that passes between the spinous processes of the C1 and C2 vertebrae and the oblique line that passes through the outer border of the upper part of the trapezius muscle. It is exactly 1 cm on either side of the vertical axis of the body, which passes through the spinous processes of the C1 and C2 vertebrae. In the upper trapezius muscle, the measurement point is between the midline and the lateral border of the acromion (Wang-Price *et al.*, 2019). In addition, measurements will be made at the zygopophyseal joint between C5-C6 intervertebral space (1/2

Cun), at the tibialis anterior muscle (Stomach 36/ST 36), at the middle part of the deltoid muscle (1-2 cm below the acromion) as well as in the levator scapula muscle (2 cm above its epiphysis, at the upper medial angle of the scapula) (Wang-Price *et al.*, 2019).

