Patients will be placed in a prone position (Fischer, 1987) for all measurements. At each aforementioned point, three measurements will be taken with the possibility of a 30-second break between measurements (Pelfort *et al.*, 2015). The first measurement will be discarded since it will be considered as a trial. The average of the two consecutive measurements (second and third) will be calculated and recorded as the final value (Wilke *et al.*, 2014; Pelfort *et al.*, 2015). The force that will be applied for the measurements will be perpendicular to the body surface and the rate of pressure increase constant at 1 kg/cm^2 per second (Reeves *et al.*, 1986; Koo *et al.*, 2013), because if it is not constant the possibility of incorrect measurement will be increased.

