# 2.9. STATISTICAL ANALYSIS

Quantitative variables will be expressed as mean and standard deviation (SD). Qualitative variables will be expressed as absolute (N) and relative (%) frequencies. Pearson's  $\chi^2$  test and Fisher's exact test (where it is necessary) will be used to compare proportions, as well as McNemar test will be used to compare the percentages of kinesiophobia between measurements. Student's t-test or nonparametric criterion Mann-Whitney will be used for the comparison of the quantitative variables between the two groups. The change in the used scales and other indicators of the participants over time will be tested using linear mixed models from which dependence coefficients ( $\beta$ ) and their Standard Errors (SE) will be obtained. The group, the measurement (endline vs baseline) and their interaction term (to be tested in which extent the change is different between measurements in the two groups), will be introduced as independent variables. In the cases, where the interaction term will be found significant, sex, age, BMI and the symptoms duration will be introduced in the model (the chosen confounding factors are the most significant), in order to be tested if the interaction remain significant. Moreover, in the case that measurements at some outcome measures will be found to differ significantly at the initial measurement between the two groups, a result not due to systematic error but found to be due to random sampling. In these cases, their initial values will be entered into the mixed linear models as an independent variable to ensure that the findings from the models are not due to the initial differences between the groups. In cases that will be found significant differences between baseline measurements, between the two groups, the initial measurements will be introduced in linear mixed models as independent variable, in order to be ensured that the findings from these models are not due to initial differences between the groups. All reported p values will be two-tailed and statistical significance will be set at p < 0.05. Analyses will be conducted using the IBM SPSS Statistics 26.0.

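### One assessor takes every baseline reading and the other every endline reading, so an assessor difference passes for an ATM effect in the before/after tests; and nothing stops the compliance form reaching the endline assessor first

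*Combined protocol and SAP*

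**What the plan says.** **Who measures.** Section 2.5.1.2 says that the first assessor "recorded the primary outcome measures, as well as the secondary outcome measure prior to the start of the study". Of the other it says: "The second assessor will administer the compliance and complaint form to the participants and will record the primary outcome measure", with the secondary measures, once the interventions are complete. The same section states that neither assessor knows the allocation, and that participants and therapists cannot be blinded.

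**What is tested.** Section 2.3 defines research question 1 as "intervention group before the intervention vs. the same group after the intervention" and labels H0A1 (PPT) a main hypothesis. H0A2-H0A4 apply the same contrast to range of motion, the deep neck flexor test and spirometry. Section 2.9 specifies a linear mixed model: "The group, the measurement (endline vs baseline) and their interaction term". It has no assessor term.

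**Reliability of the primary measure.** Section 2.5.3.1.1 states that "the pressure algometer has shown high intra-rater reliability when applied to the upper trapezius muscle" and gives a similar intra-rater figure for the suboccipital region. Within that region, "The measurement in the suboccipital region will be performed at the mastoid process and at the BL 10 point". It then adds further sites: "In addition, measurements will be made at the zygopophyseal joint between C5-C6 intervertebral space", tibialis anterior, deltoid and levator scapulae. Technique is standardised: "The force that will be applied for the measurements will be perpendicular to the body surface and the rate of pressure increase constant", the first reading is discarded and the next two are averaged.

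**The forms.** Under section 2.6 the home exercises are written on the compliance form, which is completed at the end of the ten sessions. Section 2.5.3 places the endline outcomes at completion of the interventions, at five weeks. The home exercises are ATM lessons in one arm (section 2.5.2.1) and stretches in the other (section on Group B A-S). Section 2.7 invites remarks on the interventions on the complaint form.

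**The concern.** There are two separate mechanisms.

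1. **Assessor tied to visit.** If one assessor reads systematically higher or lower than the other, every ATM patient shows that difference as change. H0A1 could then be rejected although no patient had changed. The offset could run either way, so it could mimic a benefit, mimic harm or hide a real improvement. Section 2.10 makes the before/after result the first-level conclusion on whether the method helps, so the artefact would reach the headline.

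2. **Form tied to endline assessor.** Assessor blinding is the only blinding in place when the handheld PPT reading is taken. If the assessor sees the list of home exercises before measuring, the arm is disclosed. That would bear on H0B1, the randomised main comparison, which the first mechanism leaves alone.

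**Working it through.** The plan gives no figure of its own on this point, so there is none to reproduce first.

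**Step 1: can the model separate assessor from visit?** Code group, measurement and their interaction with an intercept: four columns, rank 4. Add an assessor column. Because assessor 1 equals baseline and assessor 2 equals endline in both arms, that column duplicates measurement, and the rank stays at 4 of 5. The A-S arm does not help. If both assessors worked at both visits, the rank would be 5 of 5. This result needs no assumed number.

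**Step 2: inputs for the size.**
- ATM patients: 76 (section 2.5.1.2), or 76 × 0.8 = 60.8, so 61, after the 20% dropout in section 2.5.1.1.
- Two-sided 5% level (section 2.9).
- Assumed: constant offset b of 0.05, 0.1 or 0.2 outcome SDs; pre-post correlation r of 0.6, 0.7 or 0.8; equal SD at both visits; no true change.

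**Step 3: formula.** The SD of a change score is SD × √(2(1−r)), so the standardised shift is dz = b/√(2(1−r)). The paired t statistic is noncentral t with n−1 degrees of freedom and noncentrality dz × √n.

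Example: b = 0.2, r = 0.7, n = 61. dz = 0.2/√0.6 = 0.258; noncentrality = 0.258 × √61 = 2.02; critical value 2.00; rejection probability 0.510.

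**Step 4: false rejection of H0A1.**

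| Offset (SD) | n | r = 0.6 | r = 0.7 | r = 0.8 |
|---|---|---|---|---|
| 0.05 | 61 | 0.071 | 0.079 | 0.093 |
| 0.05 | 76 | 0.077 | 0.086 | 0.104 |
| 0.1 | 61 | 0.138 | 0.168 | 0.229 |
| 0.1 | 76 | 0.161 | 0.199 | 0.275 |
| 0.2 | 61 | 0.405 | 0.510 | 0.681 |
| 0.2 | 76 | 0.486 | 0.603 | 0.777 |

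Pooling the error over both arms (2n−2 degrees of freedom), as the mixed model would, raises these by at most 0.7 percentage points. The offset that doubles the error rate to 10% is 0.054-0.076 SD at n = 61 and 0.048-0.068 SD at n = 76.

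**Step 5: simulation, 20,000 runs, constant 0.2 SD offset.**
- Assessors split by visit: H0A1 rejected in 0.405-0.682 of runs at n = 61 and 0.487-0.772 at n = 76, in line with the table.
- Same assessor for each participant at both visits: 0.048-0.053.
- H0B1 under the present split (two-sample t on change): 0.048-0.053. A common offset cancels between arms.

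**Step 6: what the plan offers against an offset.** Of the seven PPT sites, three (mastoid process, BL 10, upper trapezius) fall in regions with a cited intra-rater figure, and four have none. No inter-rater figure is given for PPT, and that is the quantity relevant to two different assessors. Section 2.5.3.2.2 cites an inter-rater ICC of 0.86 for the deep flexor test without stating its type; some types ignore a systematic difference between raters, so it settles nothing for H0A3. No calibration or agreement check between the two assessors is described.

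**Step 7: the forms.** The compliance form and the endline outcomes fall at the same point in time and involve the same assessor, and the exercises on the form differ by arm. No section says which comes first. Neither the chance of unblinding nor its effect on readings is known, so no figure is attached.

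**The case against.** **The first mechanism leaves the randomised comparison alone.** This stands. H0A1 is an uncontrolled contrast in one arm; natural course and regression to the mean are tied to visit as well, whoever measures. The return to about 5% with a single assessor assumes those are zero, so it describes removal of the assessor artefact only. But the plan names H0A1 a main hypothesis, and existing weaknesses do not justify an avoidable one.

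**The size is assumed.** This also stands. At an offset of 0.02 SD, false rejection is only 5-6%. Widening the correlation to 0.5-0.85 widens the result at 0.2 SD to 34-88%. Standardised technique may make the offset small, but it does not show that it is zero.

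**The tests are not equally exposed.** Range of motion and spirometry are read from devices, so a plausible offset may be smaller than for handheld PPT. The confounding is the same in form. The self-completed questionnaires (H0A5-H0A11) are much less exposed.

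**The form issue is a missing detail.** This is fair: the plan requires blinded assessors, does not say that the assessor reads the form before measuring, and never calls the form arm-specific. That is inferred from its contents. The complaint form is less clear still: section 2.7 has it given before the interventions start, while section 2.5.1.2 has the second assessor administer it. These points make it a risk rather than a breach, but the plan contains nothing that prevents it.

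**Conclusion.** The concern holds on both counts. The confounding of assessor with visit in H0A1-H0A4 follows from the design alone and cannot be repaired in analysis. Its size is conditional: under the assumed correlations of 0.6-0.8, an offset of about 0.05-0.08 SD is enough to double the nominal 5% for H0A1, and 0.2 SD brings false rejection to 41-78%. No offset has been shown to exist. H0B1 is not affected by a common offset.

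The order of the forms is a separate, unquantified risk to H0B1, where assessor blinding is the only blinding. The change is cheap and should be made; neither point undermines the randomised design itself.

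**What to change.** In section 2.5.1.2:

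- Have the same one of the two existing assessors measure a given participant at baseline and endline. Assign participants to assessors before, and independently of, randomisation, for example alternately at enrolment.
- State that the compliance form is given, and any completed complaint form is seen by the assessor, only after all endline outcomes for that participant are recorded.
- Ask participants not to mention their treatment to the assessor, and withhold the baseline record sheet from the assessor at endline.

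**Cost.** Scheduling and one procedural paragraph, with no new staff. Both assessors must be available at both visits. An assessor may recall a baseline value, which the present split avoids; withholding the sheet reduces this.

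**Limits to report.** H0A1 remains an uncontrolled before/after test. The form steps close only the form route to unblinding. In the A-S arm, trigger points are inked and acupoints needled; BL 10 is named both as an acupoint and as a PPT site; and assessments take place in the same clinic as the acupuncture (section 2.5.1.3).

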### 2.5.1.3. CONDUCT OF RESEARCH - STATEMENT OF CONSENT

The technique of ATM of the Feldenkrais method will be applied at the "Mikis Theodorakis" Multipurpose Center for Cultural, Sports and Social Activities of Ilion in Athens, Greece, in collaboration with the Musculoskeletal Physiotherapy Research Laboratory of the University of West Attica (UNIWA). The acupuncture treatments, the teaching of stretching (which will then be carried out at home) as well as the assessment measurements for both interventions will be carried out in the clinic pain of the 1st Anesthesiology Clinic of the Aretaeio Hospital, in collaboration with the Musculoskeletal Physiotherapy Research Laboratory of the University of West Attica (UNIWA). All prospective patients should have a referral from their treating physician certifying a diagnosis of non-specific chronic neck pain. Before the start of the sessions, a written statement of consent will be given that patients agree to participate in the research and that they can stop at any time they wish, in accordance with the regulation of the European Union (2016/679) for the protection of personal data and the rules of medical confidentiality of the Ethics and Ethics Committee of the UNIWA.

#### 2.5.1.4. SAMPLING

The sampling of the study will follow the following steps. Starting on July 25, 2022 and until the required number of people set according to the protocol is completed, the doctors of the pain clinic of the 1st Anesthesiology Clinic of the Aretaeio hospital will assess all the patients who will come to the outpatient clinics and will be diagnosed by them with chronic non-specific neck pain or will have already a diagnosis of chronic non-specific neck pain by their treating physician. The

assessment of the patients will be carried out according to the inclusion and the exclusion criteria that will be defined in this study.

# 2.5.1.5. INCLUSION CRITERIA

The selection of the sample will be based on the criteria listed in the following table (Table 1).

Table 1. Patient inclusion criteria

- 1. Diagnosis of chronic non-specific neck pain.
- 2. Duration of the symptoms at least three months before the initial assessment and their participation in the study.
- 3. Age range 19-70 years.

## 2.5.1.6 EXCLUSION CRITERIA

Initially, a clinical examination-diagnosis of chronic non-specific neck pain will be carried out by the attending physician and then, the cases that do not meet the above inclusion criteria or meet at least one of the exclusion criteria listed in the following table (Table 2), will be excluded. The remaining patients will complete the consent form. Chronic non-specific neck pain refers to pain that is not due to a specific pathology or anatomical abnormalities. Therefore, the diagnosis will result from the exclusion of an identified or serious condition. The symptoms resemble those of Whiplash Associated Disorders (WAD) grades I and II, with the difference that the latter result from a traumatic event (Tsakitzidis *et al.* 2013). It should be noted that Table 2 also lists situations that constitute "red flags".

# Table 2. Patient exclusion criteria

- 1. History of surgical intervention in the cervical spine (Dibai Filho et al., 2017).
- 2. History of neck fracture or injury (Campa Moran *et al.*, 2015; Dibai Filho *et al.*, 2017) in the last year.
- 3. Head, face or neck surgery (Dibai Filho *et al.*, 2017)
- 4. Active cervical hernia with radicular symptoms or severe degenerative diseases in the cervical spine (Dibai Filho *et al.*, 2017)
- Systemic diseases (diagnosed rheumatic, metabolic and immunological diseases) (Edwards & Knowles, 2003; Wilke *et al.*, 2014; Campa Moran *et al.*, 2015; Cerezo Téllez *et al.*, 2016; Dibai Filho *et al.*, 2017; Cerezo Téllez *et al.*, 2018)
- 6. Myelopathy with severe disc or bone damage (Ma *et al.*, 2010; Campa Moran *et al.*, 2015)
- 7. Cervical radiculitis/radiculopathy (Ma *et al.*, 2010; Wilke *et al.*, 2014; Campa -Moran *et al.*, 2015)
- 8. Arterial dysfunction (Kerry et al., 2008)
- 9. Neoplasms active during the last five years
- 10. Lymphadenopathy (Tsakitzidis et al., 2013)
- 11. History of inflammatory arthritis (Tsakitzidis et al., 2013)
- 12. Diagnosed psychiatric illness (Wilke *et al.*, 2014; Cerezo Téllez *et al.*, 2016; Cerezo Téllez *et al.*, 2018)
- 13. Severe neurological disorder (Edwards & Knowles, 2003; Wilke *et al.*, 2014) or mental retardation (Ma *et al.*, 2010)
- Signs, symptoms or history of oral pain and temporomandibular disorders based on the Research Diagnostic Criteria of Temporomandibular Disorders -RDC/TMD (Campa - Moran *et al.*, 2015)
- 15. Fibromyalgia syndrome (Ma *et al.*, 2010; Wilke *et al.*, 2014; Cerezo -Téllez *et al.*, 2016; Cerezo Téllez *et al.*, 2018)
- 16. Infection or inflammatory swelling in the treated area
- 17. Skin damage (Edwards & Knowles, 2003) or wounds in the puncture area

(Cerezo - Téllez et al., 2016; Cerezo - Téllez et al., 2018)

- 18. Systemic intake of drugs that may affect the patient's judgment, (e.g. neuromodulators, antidepressants)
- 19. Taking systemic treatment for the same problem (Wilke *et al.*, 2014) up to three months before the study
- 20. Pregnancy (Cerezo Téllez et al., 2016; Cerezo Téllez et al., 2018)
- 21. Previous adverse reaction to acupuncture (Edwards & Knowles, 2003)
- 22. Metal allergy (Cerezo Téllez et al., 2016; Cerezo Téllez et al., 2018)
- Fear of needles (Edwards & Knowles, 2003; Campa Moran *et al.*, 2015;
   Cerezo Téllez *et al.*, 2016; Cerezo Téllez *et al.*, 2018)
- 24. Inability to express speech and writing in the Greek language

Participants who will agree to undergo the interventions, will fill out the demographic characteristics form and the questionnaires.

## 2.5.1.7. PERSONAL DATA AND DEMOGRAPHIC CHARACTERISTICS

The personal data that will be collected from each participant will be kept anonymous. Personal information, that can be used to identify the participant, at no stage of data collection will be requested, to protect their personal data inviolably. The above will be achieved with the help of pseudonymization and generalization of information that could link a pseudonym with some exclusive characteristic. For example, if the subject recorded as "Respondent 1" is 37 years old, their age is not recorded, but their age group (35-40). The procedure will be performed by a biostatistician, associate of the Musculoskeletal Physiotherapy Laboratory of UNIWA. In addition, the technique of file encryption will be followed using VeraCrypt Containers (Bursać *et al.*, 2017), i.e. the data will be placed inside a virtual disk file that with the use of "encryption keys" and the algorithm AES-256 will be converted into an unintelligible format so that they cannot be read by researchers, only by the owner of the encryption keys (biostatistician) (Loukas, 2017), protecting them during computer operation, even when they are not in use. The computer that will be used to store and process the data will be provided with a password, an encrypted hard disk to protect data at rest, from anti-electronic threat software. Moreover, the computer will be isolated in the Musculoskeletal Physiotherapy Laboratory and will not have access to the internet. This data will be stored on a computer that has been assigned a password known only to the main researcher. They will remain confidential throughout the interventions and after five years the RAM and hard drive of the computer containing all the material and/or information collected from the research will be destroyed, exposing them to microwaves and causing them to wear naturally (e.g., drill holes). All physical records that have been collected (e.g., questionnaires) will be destroyed in a special document shredder.

The demographic characteristics form includes information regarding the participant's gender, age range, body measurements (weight, height), educational level, employment status, and field of employment. In addition, it contains information on marital status, duration of symptoms, medication, and the presence of other medical condition, except for chronic non-specific neck pain. Regarding medication as well as the presence of another medical condition, they refer to drugs and diseases that are not included in the exclusion criteria.

